- 21. Clinically significant abnormal finding on the triplicate set of ECGs or evidence of any of the following cardiac conduction abnormalities at Screening (mean values will be used for the following criteria):
 - Heart rate <40 beats per minute (bpm) and >110 bpm (based on the ECG reading). NOTE: The Medical Monitor should be contacted in any instance where the Investigator is uncertain regarding the stability of a patient's medical condition(s) and the potential impact of the condition(s) on trial participation
 - Interval between Q and T wave corrected for heart rate using Fridericia's formula (QTcF) interval >450 msec for males and females
 - PR interval ≥200 msec
 - Intraventricular conduction delay with QRS duration >120 msec
 - Evidence of second- or third-degree atrioventricular block
 - Electrocardiographic evidence of complete left bundle branch block (LBBB), complete right bundle branch block (RBBB), or incomplete LBBB

Prohibited Therapies or Medications

- 22. Patients who are currently taking oral antipsychotic medications, monoamine oxidase inhibitors (MAOIs), anticonvulsants (e.g., lamotrigine, Depakote), tricyclic antidepressants (e.g., imipramine, desipramine), selective serotonin reuptake inhibitors, and any other antidepressants or any other psychoactive medications (except lorazepam, zolpidem, zaleplon, eszopiclone, or similar benzodiazepines, diphenhydramine, benztropine, and propranolol). Patients taking prohibited psychotropic medications may be eligible for inclusion in the study if it is clinically appropriate to discontinue the medication before the Baseline Visit (in the opinion of the Investigator). The prohibited psychotropic agent must be discontinued and washed out at least 5 half-lives prior to Baseline. Subjects taking a depot antipsychotic could not have received a dose of medication for at least 1 and a half injection cycles before Baseline. The medications should not be discontinued solely to make the patient eligible for enrollment in the study.
- 23. Patients who received electroconvulsive therapy within 90 days of Screening.
- 24. Patients who received Transcranial Magnetic Stimulation (TMS) within 90 days of Screening.

Confidential Page 42 of 102

Allergies and Adverse Drug Reactions

- 25. Patients with a history of neuroleptic malignant syndrome.

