The AE associated with the need for lorazepam, benztropine, or propranolol should be recorded on the Adverse Events in the eCRF. The amount and timing for each lorazepam, benztropine, or propranolol administration should be recorded for each patient.

Table 6.2:	Permitted	concomitant	medications

Medication	Study Period	Dose Permitted	Timing Restriction			
	Screening phase through Day 7	Maximum of 6 mg/day				
	Day 8 though Day 14	Maximum of 4 mg/day	Not within 12 hours prior to PANSS			
Lorazepam	Day 15 through Day 28	Maximum of 2 mg/day On no more than 4 days/Week				
Benztropine	Screening phase Through Day 28	Maximum 4 mg/day	Not within 12 hours prior to SAS, BARS, or AIMS			
Propranolol	Screening phase Through Day 28	Maximum of 40 mg/day				
Sleep Medication	Day 1 and Day 28	No restrictions ^a	Not within 8 hours prior to Cogstate test			
zolpidem, zaleplon, or eszopiclone for insomnia						

^a Allow nighttime use only (prn); exclude regular use; exclude daytime use; exclude use within 12 hours of a study visit Abbreviations: AIMS = Abnormal Involuntary Movement Scale; BARS = Barnes Akathisia Rating Scale; mg = milligram; PANSS = Positive and Negative Syndrome Scale; SAS = Simpson-Angus Scale

During the End of Stabilization period, the use of lorazepam, benztropine, and propranolol is not restricted.

Smoking is allowed, under supervision.

Confidential Page 50 of 102

Table 6.3 below provides a select list of CYP2D6 inhibitors and CYP3A4 inhibitors and inducers that are prohibited within 14 days of randomization and for the duration of the trial.

Table 6.3: Selected CYP2D6 Inhibitors and CYP3A4 Inhibitors and Inducers Prohibited During the Trial

Selected CYP2D6 Inhibitors	
Celecoxib	Methadone
Chloroquine	Moclobemide
Chlorpheniramine	Paroxetine
Clemastine	Pyrilamine
Clomipramine	Quinidine
Fluoxetine	Terbinafine
Halofantrine	Tripelennamine
Hydroxyzine	
Selected CYP3A4 Inhibitors	
Amiodarone	Fluvoxamine
Amprenavir	Indinavir
Aprepitant	Itraconazole
Chloramphenicol	Ketoconazole
Cimetidine	Nefazodone
Clarithromycin	Nelfinavir
Clotrimazole (if used orally)	Quinupristin/Dalfopristin
Delavirdine	Ritonavir
Diltiazem	Saquinavir
Erythromycin	Troleandomycin
Fluconazole	Verapamil
Selected CYP3A4 Inducers	
Carbamazepine	Phenytoin
Dexamethasone	Primidone
Efavirenz	Rifampin
Nevirapine	St. John's Wort
Oxcarbazepine	Troglitazone
Phenobarbital	

Abbreviations: CYP = cytochrome P450

Confidential Page 51 of 102

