Vital Signs ^t	X	X		X		X		X		X		
Adverse Events ^u	X	X	X	X	X	X	X	X	X	X	X	X
Other												
Study Drug Dosing		X	X	X	X	X	X	X	X	X		
PK Sample Collection ^v		X		X				X				
Restart Standard Antipsychotic ^w											X	

a. Screening begins when the ICF is signed and will take place between Day -7 and Day -1; up to a 7-day extension of the screening phase is allowed, if necessary with the approval of the Medical Monitor; screening procedures should be initiated with a sufficient amount of time allotted in order to obtain central laboratory results and ECG results from the central reader prior to randomization. Review of inclusion/exclusion criteria at Baseline will be based on assessments performed during Screening. Hospitalization will begin with the signing of the ICF for patients who are not already hospitalized at the initial Screening Visit.

Confidential Page 55 of 102

Each patient may receive the QD administration of study treatment. No other assessments are scheduled; however, AEs observed or reported, and concomitant medications may be recorded. In case of an AE, an unscheduled visit may be conducted at the discretion of the PI.

c. Stabilization Period is up to 5 days.

d. The Screening assessments to be audio recorded include the MINI 7.0.2, PCRS and SCI-PANSS and are submitted to an independent central reviewer for review and eligibility confirmation.

^{e.} Includes full psychiatric history, DSM-5 diagnosis of schizophrenia, and MINI 7.0.2.

Washout of prohibited medications begins after signing the ICF and after diagnosis of Schizophrenia is confirmed by MINI. Details of medications requiring washout and guidance for washout time required are provided in Appendix 14.4. Prohibited and restricted medications are listed in Table 6.3:

g. Urine drug screen (full panel including opioids) and a blood alcohol test are required at the designated times, but either or both can be conducted at any time during the trial at the discretion of the Investigator.

h. At Screening, Baseline, and final endpoint, SCI-PANSS and CGI-S will be evaluated by a local site rater with central supervision via independent, central review.

SCI-PANSS will be audio recorded at any visit where they are administered. SCI-PANSS assessment should be preceded by the PCRS. Patients with improvement of ≥20%

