14.4 Half-Life of Major Psychiatric Medications

The recommended duration of the washout period should be $5 \times$ the duration of the known half-life of the drug.

Half-life after oral administration (hours)
75-94
24
91
48-96 (parent drug) 7-21 days (active metabolites)
12
18-26
29-37 (at steady state)
30-38
23
57 parent drug (200 for active metabolite)
6-12
20
7 oral 2-5 IM
30
33
20
6-8 (parent drug) 12 (active metabolites)
9-12 (parent drug) 10-19 (active metabolite)
55
34

Confidential Page 100 of 102

Thioridazine	4-10 (parent drug)
	21-25 (active metabolites)
Trifluoperazine	3-12 (parent drug)
	22 (active metabolites)
Antidepressants	
Selective Serotonin Reuptake Inhibitors (SSRI)	
Citalopram	20-30
Escitalopram	
Paroxetine	
Sertraline	
Fluoxetine	1-3 days
Fluvoxamine	15
Serotonin-norepinephrine (SNRI) reuptake inhib	itors
Desvenlafaxine	9-11
Duloxetine	10-12
Levomilnacipran ER	12
Milnacipran	8-10
Venlafaxine	5 (parent)
	11 (active metabolites)
Tricyclics	
Amitriptyline	9-25
Imipramine	19
Clomipramine	12-36
Doxepin	3-80
Nortriptyline	36
Monoamine oxidase inhibitors (MAOIs)	
Tranylcypromine	2
Phenelzine	12
Isocaroxazid	36
Moclobemide	2-4
Other	
Mirtazapine	20-40

Confidential Page 101 of 102

	·
Agomelatine	1-2
Reboxetine	13
Vortioxetine	66
Benzodiazepines	
Alprazolam	12-15
Lorazepam	10-20
Oxazepam	6-20
Diazepam	36-200
Chlordiazepoxide	3 -200
Temazepam	5-15
Nitrazepam	24-40
Non-Benzodiazepine Anxiolytics	
Buspirone	2-11
T T	
Pregabalin	6
-	
Pregabalin	
Pregabalin Antiepileptics	6
Pregabalin Antiepileptics Carbamazepine	12-27
Pregabalin Antiepileptics Carbamazepine Gabapentin	6 12-27 5-7
Pregabalin Antiepileptics Carbamazepine Gabapentin Lamotrigine	6 12-27 5-7 15-35
Pregabalin Antiepileptics Carbamazepine Gabapentin Lamotrigine Levetiracetam	6 12-27 5-7 15-35 6-8
Pregabalin Antiepileptics Carbamazepine Gabapentin Lamotrigine Levetiracetam Oxcarbazepine	6 12-27 5-7 15-35 6-8 8-15
Pregabalin Antiepileptics Carbamazepine Gabapentin Lamotrigine Levetiracetam Oxcarbazepine Pregabalin	12-27 5-7 15-35 6-8 8-15 5-7
Pregabalin Antiepileptics Carbamazepine Gabapentin Lamotrigine Levetiracetam Oxcarbazepine Pregabalin Topiramate	12-27 5-7 15-35 6-8 8-15 5-7 20-30

Confidential Page 102 of 102

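### The 14-day pre-randomization ban on CYP inhibitors and inducers in Protocol section 6.7 is in no eligibility criterion, and the washout that sites are directed to (5 half-lives) is shorter for at least five of the listed drugs

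*Protocol*

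**What the plan says.** Four places in the protocol govern how long a listed drug must be stopped before randomization.

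- **Section 6.7, Table 6.3.** The selected CYP2D6 inhibitors and CYP3A4 inhibitors and inducers are "prohibited within 14 days of randomization and for the duration of the trial".
- **Section 5.2, exclusion 22.** This covers psychotropics, including antidepressants and anticonvulsants. "Patients taking prohibited psychotropic medications may be eligible for inclusion in the study if it is clinically appropriate to discontinue the medication before the Baseline". The condition is: "The prohibited psychotropic agent must be discontinued and washed out at least 5 half-lives prior to Baseline".
- **Section 7.1, washout footnote to the Schedule of Assessments.** It sets the start: "Washout of prohibited medications begins after signing the ICF and after diagnosis of Schizophrenia is confirmed by MINI". For duration it says: "Details of medications requiring washout and guidance for washout time required are provided in Appendix 14.4". It then adds: "Prohibited and restricted medications are listed in Table 6.3".
- **Appendix 14.4.** "The recommended duration of the washout period should be" five times the known half-life, followed by a half-life table for psychiatric medications.

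Two further passages set the frame. The opening of section 5 makes enrolment depend on the inclusion and exclusion criteria as met at Baseline. The screening footnote in section 7.1 fixes the time available: "Screening begins when the ICF is signed and will take place between Day -7 and Day -1", with up to 7 more days if the Medical Monitor approves.

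**The concern.** Eligibility is decided on the numbered criteria. If a pre-randomization prohibition is missing from them, and the washout time that sites are told to use is shorter than the prohibition, a site can complete its eligibility check correctly and still randomize a patient whom section 6.7 bars at that moment.

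The stakes are consistency of entry between sites and the handling of deviations. Receipt of a prohibited concomitant treatment is a named deviation category in section 10.4.1. Two sites with identical patients could act differently depending on which passage each reads as governing, and one would generate a deviation that its eligibility checklist gave no warning of. An effect on drug exposure early in dosing is possible in principle, because the banned drugs were presumably chosen for their interaction potential. The point does not depend on that effect.

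**Working it through.** There is no sample-size, power or alpha figure to reproduce. The check compares intervals and then searches the criteria.

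**Step 1. Drugs on both lists.** Washout in days = 5 × half-life in hours ÷ 24, with half-lives from Appendix 14.4. Shortfall = 14 − washout.

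| Drug (Table 6.3 and Appendix 14.4) | Half-life | 5 half-lives (days) | Shortfall against 14 days |
|---|---|---|---|
| Moclobemide | 2–4 h | 0.4–0.8 | 13.2–13.6 |
| Oxcarbazepine | 8–15 h | 1.7–3.1 | 10.9–12.3 |
| Fluvoxamine | 15 h | 3.1 | 10.9 |
| Carbamazepine | 12–27 h | 2.5–5.6 | 8.4–11.5 |
| Clomipramine | 12–36 h | 2.5–7.5 | 6.5–11.5 |
| Fluoxetine | 1–3 days | 5–15 | 9 to none (upper end is 1 day over) |

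Example: clomipramine, 5 × 36 ÷ 24 = 7.5 days; 14 − 7.5 = 6.5 days. The first five drugs therefore fall short of the ban by 6.5 to 13.6 days over their whole stated range. Fluoxetine straddles 14 days.

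The carbamazepine and oxcarbazepine values are read from row order, because that part of the table is broken in the text available. Paroxetine is also in Table 6.3 but is not counted, since its half-life cell appears merged with its neighbours. If the 20–30 h entry applies to it, 5 half-lives is 4.2 to 6.25 days and it joins the first five.

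**Step 2. Drugs only in Table 6.3.** Non-psychotropic entries such as verapamil, diltiazem, cimetidine, ketoconazole and rifampin fall outside exclusion 22 and outside an appendix of psychiatric medications. Neither place gives a washout time for them.

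**Step 3. Search of the criteria.** Inclusions 1 to 10 and exclusions 1 to 28, in both the synopsis and section 5, contain no mention of CYP drugs, of Table 6.3, or of a 14-day period. The nearest wording is inclusion 1 (able to follow requirements, including stopping prohibited medication) and inclusion 10 (willing to stop prohibited psychotropics). Neither sets an interval.

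**Step 4. Time available.** A drug stopped under the footnote, after consent on Day -7 at the earliest, has been off for at most about 7 days on Day 1. Fourteen days needs 14 − 7 = 7 more, which is essentially the whole extension.

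**Step 5. Where the window falls relative to PK sampling.** PK is sampled on Days 1, 8 and 21 in the first 60 randomized patients. Day 8 is 7 days after Day 1. A patient released at exactly 5 half-lives is then 7.4 to 12.6 days off moclobemide, oxcarbazepine, fluvoxamine or carbamazepine (0.4 + 7 to 5.6 + 7) and 9.5 to 14.5 days off clomipramine. A patient who used all 7 days of Screening for washout is 14 days off by Day 8.

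**The case against.** **The rules add up rather than conflict.** Five half-lives is a minimum in exclusion 22 and a recommendation in Appendix 14.4, and section 6.7 adds a separate prohibition. A careful site applies the longer interval and satisfies both. This stands. A reader might infer that the two rules are mutually exclusive, or that 5 half-lives releases a drug from the ban. The text supports neither reading.

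**The footnote does lead to Table 6.3.** This is also correct, and the 14-day sentence sits directly above that table, so it would be wrong to say that sites are sent only to the appendix. But the footnote cites Table 6.3 for which drugs are prohibited and Appendix 14.4 for how long.

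**Non-psychotropic drugs are not unregulated.** Section 6.7 binds wherever it sits. Medications are recorded from 30 days before Screening, and inclusion 1 asks for general compliance. So the ban is not void for these drugs. What is missing is an interval in the criteria that are checked before randomization.

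**The no-deviation rule is not engaged.** Section 5 forbids deviations from the inclusion and exclusion criteria. Since the ban is not among them, a breach is a prohibited-medication deviation and not a forbidden eligibility deviation.

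**Harm to the PK or safety data is not shown.** No passage quantifies how CYP2D6 or CYP3A4 affects LB-102. After 5 half-lives about (1/2)^5 = 1/32, or 3%, of a drug remains, so any residual effect would have to come from pharmacology outside these documents. The case is weakest for Day 8, as step 5 shows, and the primary endpoint is at Week 4. A reader might infer distorted exposure profiles; the documents allow only that an early effect is possible.

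**The extension already exists.** Screening can run to 14 days, so its length is not itself a defect. But the extension needs Medical Monitor approval, and nothing in the criteria prompts a site to request it for this reason.

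**Conclusion.** The point holds as a gap between passages. Section 6.7 imposes a 14-day pre-randomization prohibition that no eligibility criterion carries, while the criterion and appendix that do set a washout give 0.4 to 7.5 days for five of the same drugs and 5 to 15 days for a sixth. For non-psychotropic listed drugs they give none. A patient can therefore meet every listed criterion and the Appendix 14.4 washout and be randomized in breach of section 6.7.

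This rests on the half-lives as printed, including two read from row order, and on the reading that the numbered criteria are what is checked at Baseline, which section 5 supports. The number of patients affected is not known from the documents. Nothing here bears on alpha or power, and any effect on early PK or safety is unquantified.

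**What to change.** Reconcile section 6.7 with Table 6.3, exclusion 22 (synopsis and section 5.2), the washout footnote in section 7.1 and Appendix 14.4, so that one governing pre-randomization interval applies to each listed drug, including the non-psychotropic ones. Have both the eligibility criteria and the schedule footnote refer to that interval, so that it is checked before randomization. Which interval is right is for the sponsor to decide; this point takes no position on it.

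The cost is protocol wording. Depending on the sponsor's choice, there may also be a few more screen failures or Screening extensions.

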6.7.1 Acceptable Contraceptive Methods

For females of childbearing potential who may participate in the study, the following methods of contraception, if used properly and used for the duration of the study and for 30 days after the last dose of study medication, are generally considered reliable; however, if employing birth control, each couple must use 2 of the following precautions: oral contraceptives, patch contraceptives, injection contraceptives, implantable hormonal contraceptives, male condom with intravaginal spermicide, diaphragm or cervical cap with spermicide, vaginal contraceptive ring, intrauterine device or system, surgical sterilization (hysterectomy, bilateral oophorectomy, and/or bilateral salpingectomy), tubal ligation/occlusion, vasectomized partner, or sexual abstinence, if this is the patient's current practice. Contraceptive requirements do not apply to patients who are in same sex relationship, who are medically or surgically sterilized (e.g., bilateral tubal ligation, bilateral oophorectomy, hysterectomy); or practice sexual abstinence during this study.

These methods of contraception also apply to female partners of male patients.

The Investigator and each patient will determine the appropriate method of contraception for the patient during participation in the study. This will be documented at the Screening Visit in the patient's source documentation/medical record.

Male patients or male partners of female patients should not donate sperm until 90 calendar days after the last dose of study drug.

Confidential Page 52 of 102

7 STUDY CONDUCT

Unless otherwise indicated, all assessments will be performed by the Investigator or designated study personnel.

After signing the ICF, each patient will be screened to ensure eligibility for the study.

7.1 Schedule of Assessments

The study consists of a 7-day inpatients screening phase (up to a 7-day extension of the screening phase is allowed, if necessary with the approval of the Medical Monitor), Study Treatment Period (Days 1 to Day 28 including Baseline [Day 1]), Stabilization Period (up to 5 days, Days 29 to 33), and EoS Visit (Visit 7 [Day 42] ± 2 days). Therefore, the maximal study duration for an individual patient will be approximately up to 8 weeks.

Note, this is an inpatient study from Screening to the end of the Stabilization Period. The procedures to be performed throughout the study are outlined in the SoA (Table).

Confidential Page 53 of 102

Table do: Schedule of Assessments

Event	Screening Phase	Baseline	Study Treatment Period								End of Stabilization Period	End of Study Visit
Event	Up to 7 days ^a	Day 1	Days 2-7	Day 8 ±1	8 9-14	Day 15 ±1	Days 16-20	Day 21 ± 1	Days 22-27	Day 28 or ET	33°	Day 42± 2
Visit Number	1	2	NA ^b	3	NA ^b	4	NA ^b	5	NA ^b	6	7	8
Entrance/Screening Criteria												
Informed Consenta	X											
Admission to Inpatient Unit ^a	X											
Inclusion/Exclusion Criteria Review ^a	X	X										
Screening Adjudication Form(s) and Recordings ^d	X											
Medical History ^e	X											
MINI-Plus BPD 7.0.2	X											
Prior Medication Washout ^f	X											
Hepatitis/HIV	X											
Urine Drug and Blood Alcohol Screen ^g	X ^g											
Randomization		X										
Efficacy												
(PCRS) SCI-PANSS and CGI-S	X ^h	X ^h		X		X		X		Xh		
Cogstate Test	X^{i}	Xi								Xi		
Safety												
Prior and Concomitant Medication	X	X	X	X	X	X	X	X	X	X	X	X
Physical Exam ^j	X	X		X		X		X		X		X
AIMS	X	X^k		X^k		X^k		X^k		X^k		
SAS	X	X^k		X^k		X^k		X^k	_	X^k		
BARS	X	X^k		X^k		X^k		X^k		X^k		
C-SSRS	X ^l	X ^m		X ^m		X ^m		X ^m		X ^m	X ^m	X ^m
BMI and Waist Circumference ⁿ	X	X		X		X		X		X		

Page 54 of 102

	Screening Phase	Baseline Day 1	Study Treatment Period								End of Stabilization Period	End of Study Visit
Event	Up to 7 days ^a		Days 2-7	Day 8 ± 1	Days 9-14	Day 15 ± 1	Days 16-20	Day 21 ± 1	Days 22-27	Day 28 or ET	33°	Day 42± 2
Visit Number	1	2	NAb	3	NAb	4	NAb	5	NA ^b	6	7	8
Urine Pregnancy Test ^o	X	X								X	X	
Clinical Laboratories (for Screening and exclusionary purposes) ^p	X											
Hematology, Serum Chemistry including Prolactin, Urinalysis ^q	X	X		X		X		X		X		
TSH ^r	X									X		
PT, aPTT, and INR	X	X								X		
ACTH and Cortisol		X								X		
Resting 12-lead ECG ^s	X	X		X		X		X		X		
Vital Signs ^t	X	X		X		X		X		X		
Adverse Events ^u	X	X	X	X	X	X	X	X	X	X	X	X
Other												
Study Drug Dosing		X	X	X	X	X	X	X	X	X		
PK Sample Collection ^v		X		X				X				
Restart Standard Antipsychotic ^w											X	

a. Screening begins when the ICF is signed and will take place between Day -7 and Day -1; up to a 7-day extension of the screening phase is allowed, if necessary with the approval of the Medical Monitor; screening procedures should be initiated with a sufficient amount of time allotted in order to obtain central laboratory results and ECG results from the central reader prior to randomization. Review of inclusion/exclusion criteria at Baseline will be based on assessments performed during Screening. Hospitalization will begin with the signing of the ICF for patients who are not already hospitalized at the initial Screening Visit.

Confidential Page 55 of 102

Each patient may receive the QD administration of study treatment. No other assessments are scheduled; however, AEs observed or reported, and concomitant medications may be recorded. In case of an AE, an unscheduled visit may be conducted at the discretion of the PI.

c. Stabilization Period is up to 5 days.

d. The Screening assessments to be audio recorded include the MINI 7.0.2, PCRS and SCI-PANSS and are submitted to an independent central reviewer for review and eligibility confirmation.

^{e.} Includes full psychiatric history, DSM-5 diagnosis of schizophrenia, and MINI 7.0.2.

Washout of prohibited medications begins after signing the ICF and after diagnosis of Schizophrenia is confirmed by MINI. Details of medications requiring washout and guidance for washout time required are provided in Appendix 14.4. Prohibited and restricted medications are listed in Table 6.3:

g. Urine drug screen (full panel including opioids) and a blood alcohol test are required at the designated times, but either or both can be conducted at any time during the trial at the discretion of the Investigator.

h. At Screening, Baseline, and final endpoint, SCI-PANSS and CGI-S will be evaluated by a local site rater with central supervision via independent, central review.

SCI-PANSS will be audio recorded at any visit where they are administered. SCI-PANSS assessment should be preceded by the PCRS. Patients with improvement of ≥20%

in total PANSS score between the Screening and Baseline assessments will be excluded from study participation. SCI-PANSS will be administered first on visits before any other scales, when SCI-PANSS and CGI-S are being administered with the exception of Screening where MINI-Plus BPD 7.0.2 will be administered first.

The Placebo-Control Reminder Script[©] Hassman and Cohen, 2019, Version 5.0 educates clinical trial subjects of key causes of the placebo and nocebo effects, level setting of the subject's study expectations, reminding subjects what a placebo is and how that relates to their reporting of symptoms and potential side effects, and explaining how interactions with research site staff differ from their experience with clinical providers. The PCRS informs subjects that they are to be honest about their symptoms and that the site staff have no expectations of symptom improvement or worsening and will not be disappointed by the subject's responses, and asks subjects to explain in their own words PCRS content to ensure comprehension. The PANSS Rater will read the PCRS before administering the PANSS at each study visit.

- During Screening, patients will undergo a practice assessment of the Cogstate test. On Day 1 and Day 28, the actual Cogstate testing will be performed. Note: Cogstate Battery test creot be done within 8 hours of receiving a benzodiazepine or sleep medication.
- To include height at the Screening Visit only. A full physical examination will be conducted at the Screening Visit and at EoT Visit. At each other study visit, patients will be assessed for continued dosing and any possible physical symptoms and a targeted physical examination may be performed, if indicated.
- k. On Days 1, 8, 15, 21, and 28, the SAS, BARS, and AIMS assessments are to be conducted 3 to 6 hours after the administration of study treatment with the exception of ET Visit.
- 1. If the administration of C-SSRS at Screening highlights the risk of suicide not previously known, in the opinion of the Investigator, the patient should be excluded from the trial. At this visit the "Baseline/Screening" version of the C-SSRS scale will be used.
- m. At all other study visits the "Since Last Visit" version of the C-SSRS scale should be used.
- ^{n.} BMI; derived programmatically from body weight and height measurements.
- o. All positive urine pregnancy test results must be confirmed by a serum test. Patients with positive urine and serum pregnancy test results at Screening must not be enrolled. Patients with positive urine and serum pregnancy test results during the trial must discontinue treatment and be withdrawn from the trial. Pregnancy tests can be performed at any point during the trial if pregnancy is suspected.
- P. Clinical laboratory samples at Screening for exclusionary purposes are to be taken after a fast of at least 8 hours. Vital signs and ECG should be completed before any blood samples are collected. Clinical laboratory test results drawn within ± 24 hours of the scheduled timepoint may be used. Clinical laboratory tests will include the following (see Table 14.2: and Section 8.2.4):
 - Hematology Screening assessments (excluded test result) will include measurement of hemoglobin (≤9 g/dL or ≤90 g/L), platelets (≤75,000/µL or ≤75×10⁹/L), neutrophils (absolute ≤1000/µL or ≤1×10⁹/L).
 - Clinical chemistry tests for exclusionary purposes are for ALT (>2 × ULN), AST (>2 × ULN), creatinine (≥2 mg/dL or ≥176.8 μmol/L), CPK (≥3 × ULN, unless discussed with the Medical Monitor), HbA1c (≥7.0%), TSH. Important note: Free T4 will be measured only if the result for TSH is abnormal.
 - Creatinine clearance will be calculated at Screening using the Cockcroft-Gault equation; estimated creatinine clearance of <45 mL/min is exclusionary.
- Clinical laboratory samples are to be taken after a fast of at least 8 hours. Vital signs and ECG should be completed before any blood samples are collected. Clinical laboratory test results drawn within ± 24 hours of the scheduled timepoint may be used. Routine clinical laboratory tests to be monitored throughout the study will include the following:
 - Hematology will include measurement of hematocrit, RBC, reticulocytes, and WBC with differential.
 - Clinical chemistry will include measurement of albumin, ALT, ALP, amylase, AST, bicarbonate, bilirubin-total, blood urea nitrogen, calcium, creatine kinase, creatinine, gamma-glutamyl transpeptidase, globulin, glucose, lactate dehydrogenase, lipase, magnesium, phosphate, potassium, prolactin, sodium, total protein, total cholesterol, triglycerides, HDL, LDL and uric acid.
 - Urinalysis: pH of freshly voided specimen, specific gravity, protein, glucose, ketones, blood, and microscopic examination of the sediment.
- Important note: Free T4 will be measured only if the result for TSH is abnormal.
- 5. Standard 12-lead ECGs (in triplicate) will be performed after the patient has been supine and at rest for ≥5 minutes. The captured ECGs must be separated by at least 1 minute. A central ECG service will be utilized to review all ECGs in order to standardize interpretations for the safety analysis. In addition, ECG results will be evaluated at the investigational site to monitor safety during the trial. Any Screening ECG with abnormal result(s) considered to be clinically significant should be repeated to confirm the finding(s) before excluding the patient from the trial. Patients will be randomized based on Screening ECG results from the central reader and Baseline ECG results from the trial site. If the Baseline ECG results from the central reader, when available, indicate a QTcF >450 msec at Baseline, the Investigator must contact the Medical Monitor to discuss the patient's continued participation in the trial. ECGs scheduled for the same visit as blood samples are to be completed before blood is drawn.
- Vital signs will include body temperature, SBP, DBP, and heart rate. Blood pressure and heart rate will be measured in the following order: supine, sitting and standing after the patient has been in each position for at least 3 minutes. Vital signs scheduled for the same visit as blood sample have to be completed before blood is drawn.

Confidential Page 56 of 102

- The recording of AEs is to start immediately after the ICF is signed and up to 14 days after the end of EoT.
- PK analyses will include the First 60 randomized patients regardless of cohort. PK blood samples will be collected on Day 1, 8, and 21 during the following timepoints after the morning dose: 15 minutes, 30 minutes, 1, 2, 3, 4, 8, and 24 hours. See protocol Section 8.3. On Day 1 only, a pre-dose PK blood sample will be collected. Samples are collected after ECGs and vital signs. The total volume of blood to be collected during the Screening, treatment, and End of Stabilization period is 161 mL. Approximately 21 mL of blood will be collected during the Screening Visit, 130 mL will be collected during the 28-day Treatment Period, and 10 mL will be collected during the End of Stabilization period.
- w. On Day 29 patients are to be started on standard antipsychotic medication as prescribed by the Investigator.

Abbreviations: ACTH = adrenocorticotropic hormone; AE = adverse event; AIMS = Abnormal Involuntary Movement Scale; ALP = alkaline phosphatase; ALT = alanine aminotransferase; aPTT = activated partial thromboplastin time; AST = aspartate aminotransferase; BARS = Barnes Akathisia Rating Scale; BMI = body mass index; CGI-S = Clinical Global Impressions-Severity of Illness scale; CPK = creatine phosphokinase; C-SSRS = Columbia-Suicide Severity Rating Scale; DBP = diastolic blood pressure; DSM-5 = Diagnostic and Statistical Manual of Mental Disorders, Fifth Edition; ECG = electrocardiogram; EoT = end of treatment; ET = early termination; HDL = high-density lipoprotein, HIV = human immunodeficiency virus; ICF = informed consent form; INR = international normalized ratio; LDL = low-density lipoprotein; MINI 7.0.2 = Mini International Neuropsychiatric Interview version 7.0.2; MINI-Plus BPD 7.0.2 = Mini International Neuropsychiatric Interview with Borderline Personality Disorder Module version 7.0.2; NA = not applicable; PANSS = Positive and Negative Syndrome Scale; PCRS = Placebo-Control Reminder Script; PK = pharmacokinetic; PT = prothrombin time; QD = once daily; QTcF = interval between Q and T wave corrected for heart rate using Fridericia's formula; RBC = red blood cells; SAS = Simpson-Angus Scale; SBP = systolic blood pressure; SCI-PANSS= Structured Clinical Interview for the Positive and Negative Syndrome Scale; TSH = thyroid-stimulating hormone; ULN = upper limit of normal; WBC = white blood cells.

Confidential Page 57 of 102

